Safety and Effectiveness Evaluation of Eximo Medical's B-Laser™ atherectomy Device, in Subjects Affected with Infrainguinal PAD

Date:
02 Oct 2017

PRODUCT: Eximo Medical B-Laser™ for PAD

Page 1 of 5

Document number: EX-PAD-03

Revision: 02

Protocol Number	EX-PAD-03
Title	Safety and Effectiveness Evaluation of Eximo Medical's B-Laser™, an Atherectomy Device, in Subjects Affected with Infrainguinal PAD
Objective(s)	The primary objective of the study is to assess the safety and efficacy of the Eximo Medical's B-Laser™ catheter in subjects with infrainguinal peripheral artery disease (PAD)
Study Design	This is a prospective, single-arm, multi-center, open-label study.
Inclusion Criteria	
1. Subject is \geq 18 years old.2. Subject is a candidate for atherectomy for infrainguinal peripheral artery disease.3. Documented symptomatic atherosclerotic peripheral artery disease Rutherford Classification 2-4.4. Subject has an infrainguinal target lesion(s) with any type of stenosis (naïve recurrent, or in-stent) estimated to be \geq70% based on CT angiogram or any other imaging modality.5. Subject is capable and willing to comply with the scheduled follow up6. Subject or appropriate legal surrogate is able and willing to sign a written Informed Consent Form (ICF). 
Intraoperative inclusion criteria (by fluoroscopy angiogram):
 
1. Target lesion has a stenosis estimated to be \geq70%.2. In ATK subjects - at least one patent tibial run-off vessel into the foot
Exclusion Criteria	
1. Target lesion is in a vessel graft or synthetic graft.2. Target lesion length <1cm and >15 cm (in ISR cases could be >25cm).3. Endovascular or surgical procedure in the target limb performed less than or equal to 30 days prior to the index procedure OR Planned endovascular or surgical procedure 30 days after the index procedure.4. Intent to use other atherectomy device in the same procedure.5. Evidence or history of intracranial or gastrointestinal bleeding, intracranial aneurysm, myocardial infarction or stroke within the past 2 months.6. Evidence or history of aneurysm in the target vessel within the past 2 months.7. History of bleeding diathesis, coagulopathy or inability to accept blood transfusions.8. History of heparin-induced thrombocytopenia (HIT) or inability to tolerate antiplatelet medication(s), anticoagulation, or thrombolytic therapy.9. Subjects requiring dialysis.10. Known allergy to contrast agents or medications used to perform endovascular intervention that cannot be adequately pre-treated.11. Serious illness that may affect subject compliance to protocol and 30-day follow-up.12. Participating in another clinical study13. Subject is pregnant or planning to become pregnant during the study

	
period.
 
14. Life expectancy < 12 months
 
15. Any planned amputation above the ankle.
 
Intraoperative exclusion criteria (by fluoroscopy angiogram):
 
 1. Inability to intraluminally cross and secure a 0.014" wire across the target lesion. 2. Target lesion length <1cm and >15 cm (in ISR cases >25cm). 3. Reference vessel lumen diameter proximal to target lesion is <150% of the outer diameter of the B-Laser™. 4. Any clinical and/or angiographic complication prior to the planned insertion of B-laser™.

Primary Effectiveness Endpoint
	
Acute technical success:
 
Reduction from baseline in residual diameter stenosis (measured in percent), prior to any adjunctive therapy, achieved by the B-Laser™ catheter, as assessed quantitatively by the core laboratory based upon the procedure angiograms. This study's primary endpoint will be met if the mean reduction in residual diameter stenosis is greater than 20%, prior to any adjunctive therapy.


Primary Safety Endpoint
	
Freedom from the following Major Adverse Events (MAEs) through a 30-day follow-up period, as adjudicated by the Clinical Event Committee (CEC):
 
 Unplanned target limb amputation above the ankle Clinically Driven Target Lesion Revascularization (CD-TLR) Cardiovascular related deaths 
This endpoint will be met if the freedom from MAE rate is greater than 85%

Secondary Safety Endpoints
	
Freedom from the following Clinically Significant Device Related Adverse Events requiring intervention in the target vessel, as adjudicated by the CEC for up to 30 days:
 
 • Perforation • Dissection • Distal embolization or in situ thrombus • Pseudoaneurysm 
Freedom from non-Clinically Significant Device Related Adverse Events in the target vessel, as adjudicated by the CEC for up to 30 days:
 
 • Perforation • Dissection • Distal embolization or in situ thrombus • Pseudoaneurysm

Secondary Effectiveness Endpoints
	
Percent of subjects with residual stenosis by angiography of ≤ 30% post-procedure including any adjunctive therapy, with no flow limiting dissection, as adjudicated by the core laboratory.

Safety and Effectiveness Evaluation of Eximo Medical's B-Laser™ atherectomy Device, in Subjects Affected with Infrainguinal PAD

Date:
02 Oct 2017

PRODUCT: Eximo Medical B-Laser™ for PAD

Page 3 of 5

Document number: EX-PAD-03

Revision: 02

	
PAD measurements at the 30-day visit post-procedure compared to baseline:
 
• Ankle-Brachial Index (ABI)• Rutherford Classification• Walking Impairment Questionnaire (WIQ) 
Clinical success at 30 days defined as < 50% stenosis at the treated lesion, as assessed quantitatively by duplex ultrasound by the core laboratory when the peak systolic velocity ratio is < 2.5. ¹

Statistical Methodology	
Primary Effectiveness	The primary effectiveness endpoint is the reduction from baseline in residual diameter stenosis (measured in percent), prior to any adjunctive therapy, achieved by the B-Laser™ catheter, as assessed quantitatively by the core laboratory based upon the procedure angiograms. This study's primary effectiveness endpoint will be met if the mean reduction in residual diameter stenosis is greater than 20%, prior to any adjunctive therapy.
Statistical Hypothesis	The primary effectiveness hypothesis to be tested is: $H_0: \mu_{DS} \leq 20\% \text{ vs. } H_1: \mu_{DS} > 20\%$ where μ_{DS} is the mean reduction from baseline in residual diameter stenosis.
Statistical Test	The hypothesis will be tested using Analysis of Covariance (ANCOVA)
Minimum Sample Size	97 treated subjects (assuming one lesion per subject)
Primary Safety	The primary safety endpoint is the percent of subjects free of MAEs throughout the 30-day follow-up period, as adjudicated by the CEC.
Statistical Hypothesis	The primary safety hypothesis to be tested is: $H_0: \pi_{MAEF} \leq 85\% \text{ vs. } H_1: \pi_{MAEF} > 85\%$ where π_{MAEF} is the proportion of subjects free of MAEs throughout the 30-day follow-up period.
Statistical Test	The hypothesis will be tested via the lower limit of a one-sided exact binomial confidence interval.
Study Population	The trial population will consist of male and female subjects eighteen (18) years of age or older, with symptomatic infrainguinal PAD, scheduled for endovascular intervention. Subjects must also meet all other inclusion criteria and not meet any of the exclusion criteria described in Sections 5.3.1 and 5.3.2 of the Study Protocol.

¹ Per FDA request, PSVR will be presented for any subject that underwent DUS. Yet, in cases when a reference PSV is unreliable, an asterisk will be added, and the meaning of this asterisk is that true PSVR could not be calculated by the core lab and rather the core is presenting a PSVR that is using the best PSV that could be taken. The company will keep in house the records of the alternative determination of patency by the core lab in such cases that are based on correlating factors that will be used to determine stenosis (further information can be found in section 3.1 of the study protocol, PAD diagnosis, Duplex ultrasonography (DUS)).

6-Month Outcomes Analysis (from Day 36 to the end of study)	
The follow-up duration for each subject is 30-days post procedure for the primary and secondary endpoints, however subjects will be followed for 6-months post procedure.
 
At follow up visits the following parameters will be collected and recorded:
 
 • 6-Month Patency (per Lesion): Duplex Ultrasonography for core lab assessment of PSVR< 2.5. • 6-Month Clinical Presentation (per Subject): Clinical performance by Rutherford Class, ABI and WIQ • 6-Month Site-Reported Adverse Events & Serious Adverse Events • 6-Month CEC-Adjudicated Adverse Events • 6-Month Protocol Deviations 
All parameters measured after the 30-day follow-up (from Day 36 after procedure) will be summarized via descriptive statistics by data type.
				
	Visit, Number, (Time point)	Screening Visit 1 (<2m pre-procedure)	B-Laser™ procedure Visit 2 (to discharge)	Follow up Visit 3 (30d ± 5d post procedure)	Follow up Visit 4 (6m ± 2w post procedure)
	Informed consent	X			
	Assess eligibility	X			
	Medical history & demographic	X			
	Blood Tests	X			
	Con-meds	X	X	X	X
	Baseline lesion evaluation	X	X		
	Short Physical examination	X			
	Ankle-Brachial Index	X		X	X
	Rutherford Classification	X		X	X
	WIQ	X		X	X
	& Confirm eligibility per intraoperative inclusion/exclusion		X		
	PAD Intervention including B-Laser™ Atherectomy		X		
	Safety- AE, SAE, MAE, ADE		X	X	X

Safety and Effectiveness Evaluation of Eximo Medical's B-Laser™ atherectomy Device, in Subjects Affected with Infrainguinal PAD

Date:
02 Oct 2017

PRODUCT: Eximo Medical B-Laser™ for PAD

Page 5 of 5

Document number: EX-PAD-03

Revision: 02

Results	
Primary Effectiveness Results At baseline, the mean (SD) percent stenosis at the target lesion was 85.7% (12.2%). Post B-Laser™ prior to adjunctive therapy, the mean (SD) percent stenosis at the target lesion was 52.1% (14.9%). This resulted in a crude mean (SD) reduction from baseline to post B-Laser™ of 33.6% (14.2%).
 
Primary Safety Results The freedom from MAE through the 30-day follow-up period after intervention was 98.9%, with a lower limit of the one-sided 97.5% exact binomial confidence interval of 94.2%, which is greater than the pre-specified threshold of 85%, so the success criteria for this endpoint is met.

Discussion and Conclusions	
The aim of the study was to assess the safety and efficacy of the use of the Eximo Medical's B-Laser™ catheter in subjects affected with infrainguinal PAD. The study was designed to assess both safety and effectiveness of the device, and there were two hypotheses in this study.
 
The primary effectiveness endpoint was the mean reduction from baseline in residual diameter stenosis (measured in percent), prior to any adjunctive therapy, achieved by the B-Laser™ catheter, as assessed quantitatively by the core laboratory based upon the procedure angiograms. Because the lower limit of the one-sided 97.5% confidence interval was greater than 20%, we conclude that the mean reduction from baseline in diameter stenosis is > 20% prior to any adjunctive therapy, and the success criterion for this endpoint is met.
 
The primary safety endpoint is the percent of subjects free of MAEs throughout the 30-day follow-up period, as adjudicated by the Clinical Events Committee (CEC). This hypothesis was tested via the lower limit of the one-sided 97.5% exact binomial confidence interval. Because the lower limit of the confidence interval was greater than 85%, this endpoint is met.
 
Thus, the study is deemed successful as both null hypotheses (primary efficacy and primary safety endpoints) were rejected and the acceptance criteria were met. It can be claimed that Eximo Medical's B-Laser™ device is safe and effective according to its intended use.
 
The results found were quite robust. There did not appear to be statistically significant differences in the primary effectiveness endpoint across centers ($p=0.3071$) and there was only 1 non-device related MAE though 30 days, suggesting a very strong safety profile.
 
The 6-month observational outcomes showed a global improvement of the peripheral artery disease symptoms.
 
An independent Data and Safety Monitoring Board has also reviewed and evaluated the results and affirmed that based on the information that the committee was provided, the device is safe for its intended use.

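### Do the endpoint sentences set a success rule on the observed value, with a false-positive rate near 50%?

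*Combined protocol and SAP*

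**What the plan says.** All references are to the Combined protocol and SAP.

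- **Primary Safety Endpoint:** "This endpoint will be met if the freedom from MAE rate is greater than 85" per cent.
- **Primary Effectiveness Endpoint:** "primary endpoint will be met if the mean reduction in residual diameter stenosis is greater than 20" per cent. The Primary Effectiveness row under Statistical Methodology repeats this.
- **Statistical Hypothesis rows:** the effectiveness null is a mean reduction of at most 20%, with a larger reduction as the alternative. The parameter μ_DS "is the mean reduction from baseline in residual diameter stenosis". The safety null is a true MAE-free proportion of at most 85%, with a larger proportion as the alternative.
- **Statistical Test rows:** for effectiveness, "The hypothesis will be tested using Analysis of Covariance (ANCOVA"). For safety, "The hypothesis will be tested via the lower limit of a one-sided exact binomial confidence interval". Neither row gives a confidence level or alpha.
- **Results:** MAE-free rate 98.9%, one-sided 97.5% exact lower limit 94.2%; crude mean reduction 33.6% (SD 14.2%).
- **Discussion and Conclusions:** for safety, "Because the lower limit of the confidence interval was greater than 85%, this endpoint is met". Effectiveness is judged in the same way, by a one-sided 97.5% lower limit above 20%. The study is called successful because both null hypotheses were rejected.

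**The concern.** In a single-arm study against a performance goal, the success rule is the whole decision. The only forward-looking sentences that say when an endpoint is met name a mean and a rate, with no confidence limit. A population value is never observed, so a reader could apply those sentences directly to the sample figures. That rule would differ from the hypothesis tests, and it would give almost no protection against declaring success for a device that merely equals its goal.

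The one-sided 97.5% level appears only in the Results and Discussion, so the planning rows alone do not fix the bar. If the sample-value reading were the operative one, a safety result well short of statistical proof could be reported as a success.

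**Working it through.** **Inputs.** Goals of 85% and 20% (endpoint and hypothesis rows). Minimum of 97 treated subjects (Minimum Sample Size row, listed under effectiveness). One MAE (Discussion). MAE-free rate 98.9%, lower limit 94.2%, mean reduction 33.6%, SD 14.2% (Results).

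**1. Reproduce the reported safety limit.** The exact (Clopper-Pearson) lower limit for x MAE-free subjects out of n is the 0.025 quantile of Beta(x, n − x + 1). The safety denominator is not given, so solve for it with one event:

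| n | x/n | 97.5% lower limit | 95% lower limit |
|---|---|---|---|
| 93 | 98.92% | 94.15% | 95.00% |
| 94 | 98.94% | 94.21% | 95.05% |
| 97 | 98.97% | 94.39% | 95.20% |

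The reported 98.9% and 94.2% fit 93/94 (92/93 also fits after rounding). A 95% limit would have been about 95.0%, so the level used was indeed one-sided 97.5%.

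**2. Safety, chance of success at a true rate of 85%.** For each rule, find the smallest passing count r, then compute P(X ≥ r) with X ~ Binomial(n, 0.85).

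| n | Rule on observed rate | P(success) | Rule on 97.5% lower limit | P(success) |
|---|---|---|---|---|
| 97 | r = 83 (85.6%) | 0.508 | r = 90 (92.8%) | 0.016 |
| 94 | r = 80 (85.1%) | 0.559 | r = 87 (92.6%) | 0.021 |

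At a true rate of 80% and n = 97, the probabilities are 0.104 and 0.0004. With 97 subjects, counts of 83 to 89 pass the first rule and fail the second.

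**3. Effectiveness at a true mean of 20%.** If the sample mean is distributed symmetrically about 20, P(sample mean > 20) = 0.50 for any n and SD. The lower-limit rule gives 0.025. With SD 14.2 and n = 97 (crude, unadjusted), SE = 14.2/√97 = 1.442, so the observed mean must exceed 20 + 1.985 × 1.442 = 22.9%.

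**4. Both endpoints together.** The Discussion rests success on both. If both true values sat on their goals and the two results were independent, the observed-value rule would succeed with probability 0.5 × 0.508 = 0.254, not 0.5.

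**5. Which rule do the documents use?**

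- Neither endpoint sentence says observed, sample or estimate.
- The hypothesis row describes the population parameter as the mean reduction, the phrase the effectiveness success sentence uses, and sets the same 20% on it.
- The safety test row names the lower confidence limit as the test statistic. Testing a null of at most 85% by a lower limit can only mean asking whether that limit exceeds 85%.
- The Results compare 94.2% with the 85% threshold and conclude on that basis. The Discussion does the same for effectiveness with 20%. Nowhere is success declared on a point estimate.

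**6. Do the reported results depend on the reading?** Safety: 94.2% against 85%. Effectiveness, crude approximation with n = 94: SE = 14.2/√94 = 1.465, and the lower limit is 33.6 − 1.986 × 1.465 = 30.7% (also 30.7% with n = 97). Both endpoints pass under either reading.

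**The case for a change.** The strongest case for a change is that the shorthand reading still leaves the rule incomplete, because the test rows name no level. With 97 subjects, an exact one-sided limit at 97.5% requires 90 MAE-free, at 95% it requires 89, and at 90% it requires 88. The planning text does not choose between them, and the Results call only the 85% threshold pre-specified. A reader of this document alone cannot confirm that 97.5% was fixed in advance. For effectiveness the gap is wider, since naming ANCOVA does not say which estimate or limit is set against 20%.

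This stands as an observation about clarity, but it does not carry the claim of a 50% error rate. The three levels differ by two subjects in the count required, and the level applied was the strictest of the three. A one-sided 2.5% test is the usual choice, and comparing the lower limit of the adjusted mean with the goal is the natural way to test a one-sample hypothesis with a covariate. The document is also a five-page summary that refers to a separate Study Protocol, so a level absent here need not be absent there. Finally, results are already reported: editing the success sentences now with a level taken from those results would not establish what was planned, and nothing computed would change.

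**Conclusion.** The concern does not hold as a conflict between decision rules. The endpoint sentences are loosely worded, but the hypotheses, the safety test row and the reported decisions all point to one rule: the lower confidence limit must exceed the goal. Under that rule the chance of a false success at the goal is 1.6% to 2.1% for safety (97 or 94 subjects) and 2.5% for effectiveness. The figure of about 50% per endpoint belongs to a rule that the document neither tests by nor applies.

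The unstated confidence level and the unstated use of the ANCOVA estimate are missing details that the analysts filled sensibly. The study's conclusion is the same under either reading.

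This rests on a safety denominator inferred from the reported percentages and, for effectiveness, on the crude SD with 94 to 97 subjects, because the ANCOVA standard error is not given. The distance from 30.7% to 20% makes it implausible that the adjusted analysis would alter the decision.

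### Does naming ANCOVA without its terms, for a single mean in a single-arm trial, leave the primary effectiveness test unsound?

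*Combined protocol and SAP*

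**What the plan says.** All references are to the combined protocol and SAP, a five-page synopsis that also carries results.

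- **Study Design:** "This is a prospective, single-arm, multi-center, open-label study".
- **Statistical Hypothesis (Primary Effectiveness):** the null is that mu_DS is at most 20%, where mu_DS "is the mean reduction from baseline in residual diameter stenosis".
- **Statistical Test (Primary Effectiveness):** "The hypothesis will be tested using Analysis of Covariance (ANCOVA"). Nothing is added on covariates, centre, evaluation point or standard error.
- **Minimum Sample Size:** "97 treated subjects (assuming one lesion per subject").
- **Study Population:** the reader is sent to a separate document for the "exclusion criteria described in Sections 5.3.1 and 5.3.2 of the Study Protocol".
- **Results, Primary Effectiveness:** at baseline "the mean (SD) percent stenosis at the target lesion was 85.7% (12.2"%); after the laser the figures are 52.1% (14.9%). "This resulted in a crude mean (SD) reduction from baseline" of 33.6% (14.2%). No adjusted mean, standard error, lower limit or number analysed is printed.
- **Discussion and Conclusions:** the endpoint is declared met because the one-sided 97.5% lower limit exceeded 20%. A comparison across centres is reported with p=0.3071.

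**The concern.** ANCOVA is normally used to compare groups after adjustment. Here there is no second group, and the hypothesis concerns one unconditional mean. An adjusted mean in a single arm depends on where the covariate is set, how centres are weighted and which standard error is used, and the synopsis states none of these.

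The choice can matter. Suppose baseline stenosis is the covariate and the mean is read off at the sample-average baseline. The default model standard error then leaves out the sampling variation of that average. For an unconditional mean it is too small, and the one-sided error exceeds the 2.5% implied by a 97.5% limit. Adjustment done correctly gains no precision for this mean, so a one-sample t-test seems simpler and safer.

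The effectiveness conclusion rests on a lower limit that is not shown, whereas the safety result prints its rate, level and limit. A device claim appears to depend on a number that the reader cannot reproduce.

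**Working it through.** **1. Inputs.** SDs: baseline 12.2, post-laser 14.9, reduction 14.2; mean reduction 33.6 (Results). Margin 20; minimum number 97 (Statistical Methodology). The effectiveness number analysed is not printed. The safety result, "with a lower limit of the one-sided 97.5% exact binomial confidence interval of 94.2"%, with one event and a rate of 98.9%, reproduces with 93/94 (94.21%) or 92/93 (94.15%) but not with 96/97 (99.0%, 94.39%). I therefore use both 94 and 97.

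**2. The reported mean.** 85.7 − 52.1 = 33.6, as stated. The lower limit cannot be reproduced because it is not given.

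**3. Unadjusted lower limit**, mean − t × SD/√n:
- n=97: SE = 14.2/√97 = 1.442; 33.6 − 1.985 × 1.442 = 30.74; t = 13.6/1.442 = 9.4.
- n=94: SE = 14.2/√94 = 1.465; 33.6 − 1.986 × 1.465 = 30.69; t = 13.6/1.465 = 9.3.

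**4. Baseline stenosis as covariate (assumed; all three SDs from the same lesions).**
- Cov(baseline, post) = (12.2² + 14.9² − 14.2²)/2 = 84.6.
- Cov(reduction, baseline) = 12.2² − 84.6 = 64.2.
- r = 64.2/(12.2 × 14.2) = 0.371; R² = 0.137.
- SE ratio = √(1 − 0.137) = 0.929, about 7% too small. One-sided error = P(Z > 1.96 × 0.929) = 0.0344.

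Simulation at n=97 with no centre effect shows when this happens:

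| Analysis | One-sided error |
|---|---|
| Baseline ANCOVA at sample mean, default SE, unconditional inference | 0.0345 |
| Same model, conditional on the observed baselines | 0.0250 |
| Evaluated at the population mean baseline | 0.0250 |
| Variance of the covariate mean added to the SE | 0.0241–0.0252 |
| Centre only, equally weighted (five assumed layouts) | 0.0247–0.0255 |

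Only the first row, which needs four choices together, shows the 3.4%; adding equally weighted centres to that model gives 2.8% to 3.4%. The documents state none of the four. R² also comes from the trial's own results, so it does not describe the plan; assumed values of 0 to 0.20 give 2.5% to 4.0%.

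**5. The t-test under small centre differences.** With centre sizes m and intraclass correlation ρ, the variance of the mean is inflated by about 1 + (Σm²/n − 1)ρ. Centre sizes are not in the documents, so these layouts are assumptions.
- Eleven near-equal centres (nine of 9, two of 8): Σm²/n = 857/97 = 8.84. At ρ=0.01 inflation is 1.078 and error P(Z > 1.96/√1.078) = 3.0%; at ρ=0.02 inflation is 1.157 and error 3.4%.
- Six unequal centres (40, 22, 15, 10, 6, 4): Σm²/n = 2461/97 = 25.4. At ρ=0.01 inflation is 1.244 and error 3.9%; at ρ=0.02 inflation is 1.487 and error 5.4%.

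Simulation of the t-test agrees closely (2.8% to 4.0%, and 3.4% to 5.3%).

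**6. Distance from the margin.** With the estimate at 33.6, the limit reaches 20 only if the SE is 13.6/1.985 = 6.85, which is 6.85/1.442 = 4.75 times the unadjusted one. Baseline ANCOVA at the mean baseline of 85.7 gives 30.93 (n=97). Evaluated at baseline 70, it gives 22.5. It falls below 20 only for baselines under about 66%, below the 70% entry threshold.

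**The case for a change.** The strongest case for acting is about discipline. This is the primary effectiveness test, and a method named without its terms leaves the analyst free to choose them after seeing the data. Evaluation at baselines from 70 to 100 moves the lower limit from 22.5% to 35.6%, so the single word ANCOVA is compatible with limits 13 points apart. Calling the reported mean crude suggests an adjusted one exists, and it is not shown. Stating the model would cost a sentence.

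Part of this stands: from these pages nobody can reproduce the effectiveness limit or tell how many lesions it used. That is a limitation of the report. It does not show that the analysis was unspecified, because the synopsis refers to a fuller Study Protocol that is not to hand, and one-line test descriptions are normal in a synopsis. The safety test row likewise gives no confidence level.

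The 13-point range overstates the practical freedom. It requires evaluating the mean well away from the average baseline, whereas the hypothesis concerns the average over the study population. An analyst estimating that mean would evaluate at the average baseline, which returns 33.6.

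The proposed replacement is also open to challenge. A t-test assumes independent observations, and the trial is multi-centre. The centre p-value of 0.3071 neither establishes nor excludes a small centre correlation. Choosing between a t-test and an adjusted model is a trade-off on which statisticians may differ.

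**Conclusion.** The concern does not call for a change to the plan. The synopsis does omit the ANCOVA terms and does not print the effectiveness lower limit or its number analysed. The text does not establish an inflated error rate: the 3.4% needs an assumed covariate, evaluation point, standard error and mode of inference, and the only term hinted at, centre, gives about 2.5% in simulation without centre effects. Making a t-test primary would swap one conditional weakness for another of similar or greater size, with error of about 3% to 5% at assumed intraclass correlations of 0.01 to 0.02. It would also replace the prespecified method after results are known.

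The success conclusion does not turn on this point. The unadjusted lower limit is about 30.7%, more than 10 points above the margin, assuming 94 to 97 independent observations. Adjusted limits under unequal centre weighting cannot be bounded from these pages, because centre sizes are not given and the weighting could also move the estimate; but the standard error would have to be nearly five times the unadjusted one to reach 20% at the reported mean. What remains is missing detail in a summary document, of the kind the full protocol and final report ordinarily supply.

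### Does the primary effectiveness ANCOVA need a rule for subjects with more than one target lesion?

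*Combined protocol and SAP*

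**What the plan says.** All places are in the combined protocol and SAP.

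- **Statistical Methodology, Minimum Sample Size (primary effectiveness):** "97 treated subjects (assuming one lesion per subject".
- **Inclusion Criteria, item 4:** "Subject has an infrainguinal target lesion(s) with any type of stenosis". No maximum number of lesions is given in the supplied text.
- **Statistical Test (primary effectiveness):** "The hypothesis will be tested using Analysis of Covariance (ANCOVA". Covariates, unit and variance method are not listed.
- **Units named elsewhere:** for safety, "The primary safety endpoint is the percent of subjects free of MAEs throughout the 30-day follow-up period". Under 6-Month Outcomes Analysis, "6-Month Patency (per Lesion): Duplex Ultrasonography for core lab assessment of PSVR< 2.5" and "6-Month Clinical Presentation (per Subject): Clinical performance by Rutherford Class, ABI and WIQ". The secondary effectiveness endpoint on residual stenosis of 30% or less, also read by the core laboratory from angiography, is a percentage of subjects.
- **Results:** the singular is used, as in "the mean (SD) percent stenosis at the target lesion was 85.7% (12.2", with no count of subjects or lesions for effectiveness.
- **Discussion and Conclusions:** success is declared "Because the lower limit of the one-sided 97.5% confidence interval was greater than 20" percent.

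**The concern.** Diameter stenosis is measured on a lesion, not on a person. If a subject may bring two lesions and the model does not say how they enter, one permitted analysis is to stack all lesions as independent rows. Lesions in the same patient share vessel disease, operator and procedure, so their reductions are likely to be positively correlated. The standard error would then be too small, the lower limit too high, and the one-sided error rate above 2.5%. The document separates per-lesion from per-subject summaries at 6 months, so its authors knew that the two counts can differ, yet the primary effectiveness endpoint carries no such label. The sample size line also appears to rest on an assumption that eligibility does not enforce.

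**Working it through.** **Reproducing 97.** This cannot be done: planning mean, SD and power are not in the supplied text. At one-sided 0.025, n = 97 corresponds to a standardised excess over 20% of (1.960 + 0.842)/√97 = 0.284 at 80% power, or (1.960 + 1.282)/√97 = 0.329 at 90%.

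**Does allowing several lesions undermine 97 subjects?** With m lesions per subject and intra-subject correlation ICC, the design effect is 1 + (m − 1)·ICC and the effective number of observations from 97 subjects is 97m/[1 + (m − 1)·ICC]. For m = 1.1 and ICC = 0.8 this is 106.7/1.08 = 98.8. For m = 2 and ICC = 0.1 it is 194/1.10 = 176.4. It never falls below 97, so one lesion per subject is the cautious planning case. A shortfall would arise only if 97 were counted in lesions, but the text counts treated subjects.

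**What if lesions were treated as independent?** Inputs from Results: crude mean reduction 33.6, SD 14.2. Assumed: 97 subjects, a fraction f of them with two lesions, and the ICC.

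- Design effect D = 1 + ICC·2f/(1 + f)
- Type I error = P(Z > 1.96/√D)
- Number of lesions N = 97(1 + f)
- Lower limit, independent = 33.6 − t(N−1)·14.2/√N
- Lower limit, clustered = 33.6 − t(96)·14.2·√(D/N)

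| f | ICC | D | Type I error | Limit, independent | Limit, clustered | Shift |
|---|---|---|---|---|---|---|
| 0 | any | 1.000 | 2.5% | 30.74 | 30.74 | 0 |
| 0.1 | 0.5 | 1.091 | 3.0% | 30.87 | 30.75 | 0.12 |
| 0.3 | 0.5 | 1.231 | 3.9% | 31.10 | 30.82 | 0.28 |
| 0.3 | 0.7 | 1.323 | 4.4% | 31.10 | 30.71 | 0.39 |

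A simulation at a true mean of 20 (40,000 trials per row) gave 2.5%, 3.0%, 3.8% and 4.6% with lesions as independent. Subject-clustered standard errors gave 2.5%, 2.5%, 2.5% and 2.7%, and subject means gave 2.5%, 2.4%, 2.4% and 2.6%. Either customary treatment therefore holds the error rate close to nominal.

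**A harsher case.** Suppose only 97 lesions in all, two per subject, ICC 0.8, so D = 1.8. The limit is 33.6 − 1.985·14.2·√(1.8/97) = 29.8. The type I error without adjustment would be 7.2%.

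**Distance to the threshold.** The design effect at which the limit would reach 20 is [(33.6 − 20)/(1.96·14.2/√97)]² = 23.2. With two lesions per subject D cannot exceed 2.

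**Reading the text for the unit.** The closest analogue, the secondary angiographic endpoint, is per subject. The sample size line, placed directly below the ANCOVA line, takes one lesion per subject. The intraoperative criteria and the results speak of the target lesion in the singular. Together these point to one value per subject. The per-lesion label on 6-month patency points the other way, so this reading is likely but not proven.

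**The case for a change.** The strongest case for a change is that this is the primary endpoint. The authors treated one lesion per subject as an assumption and not as a rule, and the singular wording is description, not an analysis rule. Without a lesion count a reader cannot tell which analysis produced the reported limit. The remedy would cost one sentence and one standard error option, and an error rate of 3.0% to 4.4%, or 7.2% in the harsher case, would matter in a trial with a close result.

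The factual part stands: the supplied text states no unit for the primary ANCOVA. Three things weaken the rest.

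- The harm needs three facts together: subjects with several lesions, a lesion-level analysis, and no allowance for clustering. None is documented.
- The supplied text is a five-page synopsis with one line per method, and it refers to a fuller Study Protocol that is not included. Calling 33.6% a crude reduction and reporting a comparison across centers (p = 0.3071) both suggest that more model detail exists than is shown. Absence here does not establish absence from the plan.
- A subject mean, an index lesion, a random subject intercept and a clustered standard error would all be acceptable once stated. The request is therefore to write a rule down, not to replace a wrong method. Because results are already reported, a sentence added now could not restore pre-specification.

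**Conclusion.** No change follows. The missing unit is a gap in detail that an analyst would ordinarily fill with one value per subject or a subject-clustered variance, and both keep the error rate close to 2.5%. The contrast with the sample size is not a defect, since more lesions in 97 subjects cannot reduce the information when clustering is modelled. Even if lesions had been treated as independent, the overstatement of the lower limit is at most about 0.4 points in the tabulated scenarios, against a margin of about 10.7 points (30.7 − 20), so the conclusion against 20% stands.

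This rests on assumed lesion counts, ICC and 97 analysed subjects, and on one-sample t limits from the crude SD as an approximation to the ANCOVA limit. The denominator matters little. One event with a 98.9% rate and a 94.2% exact limit fits about 93 to 94 subjects for safety; with 93, the limit for the mean reduction would be 30.68 rather than 30.74.
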